## 9.2 Planned recruitment rate

We plan to recruit physicians through the collaborating laboratories. We have no data on the rate with which we can expect to recruit the required amount of physicians. In an ongoing trial on decision support in primary care the required amount of 120 physicians out of 1000 eligible physicians was accomplished within 4 weeks of the first invitation. The amount of eligible physicians in our trial is around 2000, suggesting that it should be feasible to recruit 300 physicians within 2 weeks of the first invitation.

We have estimated that each study physician orders 15 laboratory panels per week for the 17 conditions or indications included in our study. This is a conservative estimate ensuring that we will be able to analyse sufficient data after the 3 month period. For the outcome of appropriateness we need to analyse at least **7305** tests (for a three month period, this would be the amount of tests ordered by **35** physicians). We need these three months to expose at least 12 600 patients (42 patients x 300 physicians) to our intervention for whom we will collect data on missed diagnoses. In case the rate of patient exposure were to be slower than expected, we will prolong the intervention period to include at least 12 600 patients.

## 9.3 Statistical analysis plan

Full details of the statistical analysis will be described in a Statistical Analysis Plan which will be finalised prior to database lock.

### 9.3.1 Summary of baseline data and flow of patients

For the comparison of PCP characteristics, continuous data will be presented by their average and standard deviation or median and interquartile range and comparisons between the allocated groups will be done using a t-test or Wilcoxon or rank-sum test, as appropriate)

For comparisons of physician characteristics, comparisons will be made using generalised estimating equations (GEE), using PCP as the clustering variable. An independent working correlation matrix will be used to account for correlations with the clusters. For continuous variables, an identity link and normal distribution will be used; for binary variables, a logit link and binary distribution; for categorical variables, a cumulative logit link and multinomial distribution. Means and proportions per group will be estimated from the model.

For the comparison of patient characteristics, similar methodology will be used as for physician characteristics, but using physician as the clustering variable.

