# 9 STATISTICS AND DATA ANALYSIS

## 9.1 Sample size calculation

Our study involves multiple levels which are not independent of each other. Lowest on the level of analysis is the individual laboratory test included in our study. We must account for the fact that these tests are not ordered entirely independent of each other in one patient, for instance, a white blood cell count is often ordered together with a white blood cell differentiation. In our analysis we will account for this level of clustering. Additionally, there is clustering on the level of the physician. When the same physician orders tests for various patients over time, each of these orders is not independent of the other. For instance, if a physician often requests chloride in patients taking diuretics, then this will probably be so in all patients taking diuretics. We must therefore also account for clustering on the level of the physician. Finally, GP's often work in primary care practices. Physicians working in the same practice tend to have similar ordering behaviour implying that the orders made by two physicians in the same practice are not independent of each other. This is the last level of clustering for which we will account. We therefore have a 4 level setting comprising test, patient, physician and primary care practice:

1. Multiple study tests per patient, assumed to be 5 per patient,
2. Multiple patients per physicians, assumed to be 42 per 3 months if there is 70% use of the online intervention,
3. Multiple physicians per primary care practice (PCP), assumed to be 2.35 based on preliminary data by Heselmans et al ([Heselmans 2013](#)).

Each of these clustering levels inflates the required sample size.

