Figures and statistics on appropriateness of laboratory testing are grossly lacking, due to heterogeneity in the definition of appropriateness and differences in appropriateness criteria depending on the type of test. A robust figure, that seems reiterated in various studies, is that the proportion inappropriate laboratory tests is found to be around 30% (Zhi 2013, van Walraven 1998). It is believed that when using order sets in a CPOE, the appropriateness of laboratory ordering will improve. We propose that the trial should have 80% power to detect a 10% difference (in this case, from 30% to 20%) using a significance level of 5%. Appropriateness will be measured as the proportion of inappropriate study tests recorded through the CPOE. The unit of randomization is the PCP and not the patient or test, hence it is necessary to account for the lack of independence between the various tests, patients treated by the same physician and physicians working in the same PCP. In our design we account for clustering on multiple levels; clustering on the level of the individual tests ordered for the same patient, clustering for ordering patterns of the same physician for different patients and clustering for ordering patterns of physicians practicing within the same PCP. Estimates of intraclass correlation coefficients (ICCs) for process of care measures in primary care are between 0.05 and 0.15 (Campbell 1999, Campbell 2000), however estimates for ICCs regarding appropriateness of laboratory tests have been shown to vary between 0.04 and 0.288 (Littenberg 2006). To our knowledge no ICCs have been published for clustering on the various levels observed in our trial, therefore we have chosen to use a very conservative ICC estimate of 0.2 for each level of clustering in our sample size calculations, probably overestimating the design effect. Using methods proposed by Campbell (Campbell 2004) we would need 586 tests over both arms if unadjusted for clustering. We hypothesize that each panel will include approximately 5 study tests and that physicians will order laboratory tests for 42 patients per 3 months using the CPOE, assuming a 70% usage of the CPOE (van Wijk 2001). To account for clustering on the PCP level, we assume 2.35 physicians per PCP based on preliminary data from an ongoing trial (Heselmans 2013). In this situation the amount of tests would be inflated to 7305 tests, or 35 physicians in a trial lasting 3 months, taking into account multi-level clustering and attenuation of the clustering due to the amount of measures per patient (Teerenstra 2008). Figure 15 summarises the sample size calculations for the outcome appropriateness and their assumptions.

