
Sample size for comparison of 2 proportions (binary values): 2-sided equality

Appropriateness: pA: 70%

Clinically significant change of 10% (to pB: 80%)

$\alpha = 0.05$

$1-\beta = 0.80$

$K = 1$

Sample size: 586

Sample size calculations based on Campbell et al (Campbell 2004) for a trial with 80% power to detect a difference of 10% (increase of appropriateness from 70% to 80%) with a significance of 10% predict 586 tests.

Design effect of clustering on sample size based on Teerenstra et al (Teerenstra 2008):

4 level setting comprising test, patient, physician and primary care practice:

1. Multiple study tests per patient, assumed to be 5 per patient,
2. Multiple patients per physicians, assumed to be 42 per 3 months if there is 70% use of the online intervention and 1/3 indications included in the study,
3. Multiple physicians per primary care practice (PCP), assumed to be 2.35 based on preliminary data by Heselmans et al. (Heselmans 2013)

We assume an intracluster coefficient of 0.2 for each level of clustering.

$Rho_n$  = correlation between two physicians active in the same PCP

$Rho_s$  = correlation between two patients cared for by the same physician

$Rho_e$  = correlation between two tests ordered for the same patient

$n_n$  = mean amount of physicians per PCP

$n_s$  = mean amount of patients per physician

$n_e$  = mean amount of study tests per patient

$Phi_e = 1 + Rho_e * (n_e - 1)$

$Phi_s = 1 + Rho_s * (n_s - 1) * w_e$

$Phi_n = 1 + Rho_n * (n_n - 1) * w_n$

$w_e = (n_e * Rho_e) / (1 + Rho_e * (n_e - 1))$

$w_s = (n_s * Rho_s) / (1 + Rho_s * (n_s - 1))$

The final design effect (DE) =  $Phi_e * Phi_s * Phi_n$

Applied to our protocol:

$n_n$  = mean amount of physicians per PCP = 2.35

$n_s$  = mean amount of patients per physician = 42 per 3 months

$n_e$  = mean amount of study tests per patient = 5

$Phi_e = 1 + Rho_e * (n_e - 1) = 1.8$

$Phi_s = 1 + Rho_s * (n_s - 1) * w_e = 5.56$

$Phi_n = 1 + Rho_n * (n_n - 1) * w_n = 1.25$

$w_e = (n_e * Rho_e) / (1 + Rho_e * (n_e - 1)) = 0.56$

$w_s = (n_s * Rho_s) / (1 + Rho_s * (n_s - 1)) = 0.913$

The final design effect (DE) =  $Phi_e * Phi_s * Phi_n = 1.8 * 5.56 * 1.25 = 12.465$

586 test \* 12.465 (DE) = 7305 test = 1460 patients = 35 physicians during 3 months

Figure 15: Sample size calculations for primary outcome appropriateness including inflation due to multi-level clustering

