3.2. Randomisation

Participating PCPs were randomised to the intervention or to the control group. The unit of allocation is the PCP. This means that all physicians in the same practice were allocated to the same intervention and that either all or no physicians in the PCP were included in the trial. All patients cared for by the same primary care practice were exposed to the same intervention. We recruited 288 physicians on 01/12/2017 of which 8 physicians dropped out before including patients. The 280 physicians were distributed across 72 PCPs. We stratified the randomisation according to the laboratory with which they collaborated (3 strata). The level of confidence in using a CPOE was associated with the laboratory with which the PCP collaborated. This also assured that all PCPs collaborating with a laboratory were evenly distributed across both arms. Randomisation was done using a random numbers generator by the trial chief statistician. The research team will remain blinded to the allocation until after database lock. Further details on the randomisation scheme can be found in the protocol under 8.3.

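### Protocol 9.3.1 compares patient characteristics between arms with physician as the cluster although practices were randomised, so the standard errors are too small if patients within a practice are alike

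*Protocol*

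**What the plan says.** Protocol 9.3.1 sets out the baseline comparisons. For physician characteristics, "comparisons will be made using generalised estimating equations (GEE), using PCP as the clustering variable", with an independence working correlation matrix. For patients the level drops: "For the comparison of patient characteristics, similar methodology will be used as for physician characteristics, but using physician as the clustering variable".

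Both documents place randomisation at the practice. Protocol 9.1.1: "The unit of randomization is the PCP and not the patient or test". SAP 3.2: "The unit of allocation is the PCP". Protocol 9.1 also says why the practice level matters for ordering: "Physicians working in the same practice tend to have similar ordering behaviour".

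SAP 10.2.1 and 10.2.2 use PCP as the cluster in every outcome model they specify. This moves the primary outcome up from patient (Protocol 9.3.2) and test volume up from physician (Protocol 9.3.3.2). The SAP has no section on baseline comparisons.

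**The concern.** With an independence working correlation, clustering enters a GEE only through the empirical (sandwich) standard error, and the named cluster decides which covariances are counted. Naming physician treats physicians of the same practice as independent, although the whole practice was allocated together. If patients of colleagues in one practice resemble each other in age, sex or other characteristics, as would happen with a shared catchment area, that covariance is missing and the comparison flags chance differences too often.

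Patient comparability carries more weight here than in an individually randomised trial. Patients entered, and were asked for consent, after allocation (Protocol 8.2), through physicians who knew their arm from the start of the study (Protocol 8.3.1). At stake is how a table of patient characteristics would be read, not an estimate of effect.

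**Working it through.** **Inputs**

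- Physicians per PCP, k. Planned: "mean amount of physicians per PCP = 2.35" (Protocol 9.1.1). Achieved: "The 280 physicians were distributed across 72 PCPs" (SAP 3.2), so 280/72 = 3.89.
- Patients per physician, m. Planned: "mean amount of patients per physician = 42 per 3 months" (Protocol 9.1.1). Achieved: 11,200/280 = 40 (SAP 3.3).
- ICC: 0.2 at each level in Protocol 9.1.1, given for appropriateness. None is given for patient characteristics.
- Significance level for baseline comparisons: not stated; 5% two-sided assumed.

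**Step 1: reproduce the plan's PCP-level factor.** Figure 15 of the protocol gives Phi_n = 1.25. The printed formula uses a weight w_n that is not defined; the defined w_s reproduces the figure.

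- w_s = 42 × 0.2 / (1 + 0.2 × 41) = 0.913
- Phi_n = 1 + 0.2 × (2.35 − 1) × 0.913 = 1.2465
- Design effect = 1.8 × 5.556 × 1.2465 = 12.465, as printed

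**Step 2: what clustering on physician leaves out.** Let ρ be the ICC among patients of one physician, and sρ the correlation between patients of different physicians in one PCP, so that s is the share carried over.

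- Variance factor with PCP as cluster: 1 + (m − 1)ρ + (k − 1)m·sρ
- Variance factor with physician as cluster: 1 + (m − 1)ρ
- Ratio: R = 1 + (k − 1)·s·w, where w = mρ / (1 + (m − 1)ρ)
- Actual rejection rate of a nominal 5% test: 2[1 − Φ(1.96/√R)]

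Phi_n is this ratio with s = 0.2 and ρ = 0.2.

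**Step 3: the protocol's own correlation structure, borrowed from appropriateness.**

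- Planned sizes: R = 1.25, standard error 10% too small, rejection rate 7.9%.
- Achieved sizes: w = 8/8.8 = 0.909; R = 1 + 0.2 × 2.889 × 0.909 = 1.53; standard error 19% too small; rejection rate 11.3%.

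**Step 4: sensitivity at the achieved sizes (k = 3.89, m = 40; all ICCs assumed).** Example with ρ = 0.05 and s = 25%: w = 2/2.95 = 0.678; R = 1 + 2.889 × 0.25 × 0.678 = 1.49; rejection rate 10.8%.

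| Share s | ρ = 0.025 | ρ = 0.05 | ρ = 0.1 | ρ = 0.2 |
|---|---|---|---|---|
| 0% | 5.0% | 5.0% | 5.0% | 5.0% |
| 10% | 6.7% | 7.3% | 7.8% | 8.1% |
| 25% | 9.4% | 10.8% | 12.0% | 12.8% |
| 50% | 13.6% | 16.4% | 18.4% | 19.8% |

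At the planned sizes (k = 2.35, m = 42) the 10%, 25% and 50% rows would span 5.8–6.4%, 7.1–8.7% and 9.2–12.3%.

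**Step 5: the extreme, s = 100%.** With equal physician and practice ICCs of 0.01 / 0.02 / 0.05, the correct standard error is 1.35 / 1.52 / 1.72 times the physician-clustered one, and the rejection rate is 15% / 20% / 25%. This assumes that physicians add no variation of their own.

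**Step 6: simulation.** An independence GEE with identity link and sandwich standard errors was run for 72 PCPs and 280 physicians, with ICC 0.05 or 0.2 and 4,000 replicates. Clustering on physician rejected 9.8–19.9% of the time with equal PCP sizes and 13.2–28.5% with unequal sizes when 20% or 50% was shared, and about 5% when nothing was shared. Clustering on PCP, across all of these settings, rejected 5.4–6.0% with equal sizes and 5.9–7.7% with unequal sizes. The documents give no distribution of practice sizes, so the unequal case is also an assumption.

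**The case against.** **The comparison may no longer be planned.** SAP section 7 confines the work to the final analyses that the SAP itself defines, and SAP section 10 defines no between-arm comparison of patient characteristics. On that reading only descriptive demographics remain; SAP 6.4.1 mentions reporting of this kind. Against this, SAP 2.1 presents the SAP as an elaboration of the protocol's plan, and nothing withdraws 9.3.1. This part of the objection stands: the documents do not settle the matter.

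**It is not declared a selection check.** A reader might infer that this is the trial's test for differential recruitment. Neither document says so. Protocol 9.3.1 gives no threshold or decision rule, and Protocol 8.6 lists only practice and physician items as baseline data. The design makes the comparison relevant to selection, but that purpose is an inference.

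**The size is unknown.** This also stands. The 15–25% figures need the extreme assumption of Step 5, and weak sharing gives only 7–8%.

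**The protocol argues against practice-level clustering.** Protocol 9.1.2 does so only for missed diagnoses, in the sample size calculation. It gives no such argument for patient characteristics, and Protocol 9.3.3.1 clusters even missed diagnoses on PCP.

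**Conclusion.** The cluster named in Protocol 9.3.1 lies below the unit of randomisation and does not match the sentence before it. The direction of the error is certain for any positive correlation between patients of different physicians in one practice; only zero correlation leaves the test at 5%. At the achieved cluster sizes the rejection rate is plausibly about 7–20% when 10–50% of the physician-level ICC is shared, and 15–25% in the extreme case. All of this rests on assumed ICCs. The achieved 3.89 physicians per practice, against 2.35 planned, makes it worse.

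A reader might go further and conclude that the trial's findings are undermined. The documents do not support that. The SAP outcome models, including the non-inferiority analysis, cluster on PCP, and the adjusted analyses in Protocol 9.5 use covariates named in advance rather than chosen from baseline tests. Nor would a real difference be hidden: a standard error that is too small makes it more likely to be flagged. The harm is limited to false positives in a comparison of patient characteristics. The point is minor.

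**What to change.** State in a short SAP baseline section, or in Protocol 9.3.1, whether patient characteristics will be compared between arms. If so, name PCP as the clustering variable. A small-sample correction to the sandwich variance is preferable, because plain PCP clustering with 72 practices of unequal size still rejected 5.9–7.7% in simulation. If only descriptive demographics are intended, say so and withdraw the 9.3.1 comparison.

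The cost is one changed term in the model statement and wider intervals. No new data are needed: SAP 6.4.1 already plans a physician identifier that carries the practice.

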### 9.3.2 Primary outcome analysis

To assess differences between the allocated groups in the proportion appropriate tests, a logistic GEE model will be used: of interest are the marginal proportions, not the individual probabilities of test to be appropriate.

The logistic GEE model will include the allocated group as a factor and patients as the clustering variable. The effect of the intervention will be expressed as the difference in proportions and will be presented together with its associated 95% confidence interval. The proportion of appropriate tests in the two allocated groups will also be estimated from the GEE model and presented with their 95% confidence intervals.

Appropriateness for the composite of all study tests will be compared between intervention and control groups groups. Furthermore, an analysis will be performed that only includes patients who have no indications in addition to the 17 study indications. This additional analysis will correct for an overestimation of inappropriate tests when more than one indication is selected, including indications not under evaluation. These tests would be considered inappropriate even though they could be appropriate according to one of the other indications not being evaluated.

The analyses will be performed on all patients from all physicians according to their allocated group.

### 9.3.3 Secondary outcome analysis

#### 9.3.3.1 Missed diagnoses

The proportion of patients with a missed diagnosis will be analysed by means of a logistic GEE model that includes a factor for allocated group and uses PCP as the clustering variable. An independent working correlation matrix will be used. The proportion of patients with a missed diagnosis and associated 95% confidence intervals will be estimated from the model.

The difference in proportions will be obtained by subtracting the two proportion. The associated standard error will be calculated from the rules for the variance of a difference between two independent estimates. The 95% confidence interval for the difference will be calculated.

The non-inferiority limit for missed diagnoses is 1%, i.e. the intervention will be deemed non-inferior if the difference between the allocated groups (intervention – control) is less than 1%. Therefore, the intervention will be deemed non-inferior if the upper limit of the 95% confidence interval lies below 1.

As for the primary endpoint, the analysis will be performed for all 17 study indications together. An analysis will be performed that only includes patients who have no indications in addition to the 17 study indications

### 9.3.3.2 Test volume

The total number of tests will be analysed using a Poisson GEE model that includes allocated group as factor in the model and physician as clustering variable. No offset will be used. The number of tests per patient for each group will be estimated from the model and presented together with their associated 95% confidence intervals. The effect of the intervention will be presented as the ratio between the two numbers with its 95% confidence interval. Statistical significance will be assessed at a significance level of 5%.

### 9.3.4 Exploratory outcome analysis

#### 9.3.4.1 Downstream or cascade activities

The total number of cascades per patient will be analysed using the same methodology as for the total number of tests (see section 9.3.3.2).

## 9.4 Subgroup analyses

Subgroup analyses per indication will be done for the primary outcome and for the proportion of patients with missed diagnosis. In addition, an analysis will be performed that only includes patients who have no indications in addition to the 17 study indications.

## 9.5 Adjusted analysis

For the primary endpoint and the missed diagnoses, the following adjusted analyses will be performed:

- Volume of physician practice, i.e. the total number of tests prescribed the previous year.
- Total number of patients in practice
- Physician's age or years worked.

## 9.6 Interim analysis and criteria for the premature termination of the trial

The intervention period will last 6 months, with a first data collection after 3 months, and there is little or no risk of adverse effects. We do not foresee an interim analysis and any criteria for premature termination of the trial. In case a physician is prompted to order a series of tests he does not agree with, then he is free to order other or additional tests. This range of freedom should avoid potentially hazardous situations in the improbable situation that this should arise.

## 9.7 Subject population

We will include all data for test orders ordered through the CPOE. Tests ordered through paper-based order forms will not be included in the analysis as these orders were not subject to the intervention. Of the paper-based orders, a significant amount will be orders made during house calls or situations in which a computerized order entry is not feasible. Additionally, orders through a paper-based order form lack information on the indication for the tests making it impossible to assess whether these tests are (in)appropriate. We will monitor the number of paper-based orders as a measure of implementation success of the CPOE.

